### 7.7.2 Analyses of Secondary Efficacy Endpoints

Analyses of the secondary efficacy endpoints will be conducted at the conclusion of Part 2.

The key secondary endpoint is the incidence of RRT from Day 1 to Day 28, inclusive with patients who die or withdraw from the study during this period without recording RRT incidence being counted as having not required RRT. This endpoint will be summarized by treatment group using counts and percentages. Should a statistically significant result be obtained from the combination test analysis of the primary endpoint, the optimal recAP dose will be formally compared with placebo using a logistic regression model with treatment group and site as explanatory variables. Otherwise the results will be reported as exploratory analyses only. The odds ratio and associated 95% confidence interval from this comparison will also be presented.

The above summarization and analysis will also be repeated, excluding those patients who die or withdraw from the study from Day 1 to Day 28, inclusive. Should statistically significant results not be obtained from both the primary endpoint and the key secondary endpoint, the results from the logistic regression model for this comparison will be reported as exploratory analyses only.

Descriptive statistics will be used for all other continuous secondary efficacy endpoints, summarizing absolute values and/or change from baseline as required across all four treatment groups in tables and/or figures as appropriate. Categorical secondary efficacy endpoints will be summarized for the treatment groups by counts and percentages, and shift tables as appropriate. Selected endpoints will be analyzed by appropriate methods; these analyses will be exploratory only and defined in more detail in the SAP.

### **7.7.3 Safety Analyses**

The safety summaries will include all 4 treatment groups, comprising all patients in the safety set.

Treatment-emergent adverse events will be tabulated by treatment group. The number and percentage of patients with at least 1 TEAE will be presented along with a breakdown by system organ class and preferred term, with each patient being counted once at each summarization level. This summary will be repeated for treatment-related TEAEs, TEAEs that lead to study drug discontinuation, by relationship to study drug, by intensity, and for treatment-emergent SAEs.

Laboratory test results (for hematology, clinical chemistry, and urinalysis parameters not considered in the efficacy analyses), vital signs data, and ECG data will be presented in tables summarizing absolute values and change from baseline by treatment group, with shift tables included as appropriate. Other safety data will be listed only.

#### **7.7.4 Pharmacokinetic Analyses**

A population PK analysis of plasma concentration-time data will be performed using non-linear mixed-effects modeling. Data from this study may be combined with data from an additional study in healthy adult volunteers and included in an integrated PK analysis. The structural model will contain clearance and volume of distribution as fixed-effect parameters. The intersubject variability in the parameter estimates and the random residual error in the data will be estimated with an appropriate error model. Available patient characteristics will be tested as potential covariates affecting PK parameters. Details of the analysis will be given in a population PK analysis plan and the results of the population PK analysis will be presented in a separate report.

#### **7.7.5 Other Analyses**

Information from any additional, baseline, or screening assessments (e.g., disposition of patients, demographics, previous medical history, site of infection and pathogen, APACHE II score, SAPS-2, AP levels) will be listed and, where appropriate, presented by means of descriptive statistics for continuous variables, or frequency counts and percentages for categorical variables.

#### **7.7.6 Interim Analyses**

An unblinded interim analysis will be conducted on the Part 1 data to determine the optimal recAP dose for Part 2. This analysis will compare the 4 treatment groups from Part 1 on the primary efficacy endpoint, and a selection of the safety data. Further details on the data required will be specified in the DMC charter and the interim analysis plan. The interim analysis will be conducted on all data collected up to the first 7 days of laboratory data of the 120th patient from Part 1.

To maintain the blind, the interim analysis will be conducted and delivered by an unblinded PPD Biostatistics team located at a different site to the blinded PPD biostatistics personnel involved in the study. The results will be reviewed by an independent DMC, who will make

the dose selection decision. The type 1 error rate will be controlled by combining the results for the primary efficacy endpoint from the interim analysis (Part 1) and the final analysis (Part 2) using the inverse normal method described in Section 7.7.1. A futility analysis will also be conducted at the interim analysis. If none of the 3 recAP doses in Part 1 show evidence of efficacy (i.e., all 3 groups have 1-sided, unadjusted p-value greater than 0.8), then the study will be terminated.

## **7.8 Data Quality Assurance**

The sites will maintain source documentation and enter patient data into the eCRF as accurately as possible and will rapidly respond to any reported discrepancies. Electronic CRFs are accessed through Medidata Rave® (Medidata Solutions Inc, New York, New York). This electronic data capture system is validated and compliant with US Title 21 Code of Federal Regulations (CFR) Part 11. Each person involved with the study will have an individual user name and password that allows for record traceability. Thus, the system, and subsequently any investigative reviews, can identify coordinators, investigators, and individuals who have entered or modified records, as well as the time and date of any modifications. A quality review of the data will be performed by the site with additional reviews by the clinical monitor through source data verification.

Each eCRF is presented as an electronic copy, allowing data entry by study site staff, who can add and edit data, identify, and resolve discrepancies, and view records. This system provides immediate direct data transfer to the database, as well as immediate detection of discrepancies, enabling site coordinators to resolve and manage discrepancies in a timely manner.

Paper copies of the eCRFs and other database reports may be printed by the investigator. This system provides study site staff, monitors, and reviewers with access to hard copy audits, discrepancy reviews, and investigator comment information.

After all data reviews and query resolutions are complete, the statistical analysis plan approved and signed, and any summary/analysis populations approved, the database will be locked.

## **7.8.1 Data Management**

As part of the responsibilities assumed by participating in the study, the investigator agrees to maintain adequate case histories for the patients treated as part of the research under this protocol. The investigator agrees to maintain accurate eCRFs and source documentation as part of the case histories. These source documents may include diary cards, laboratory reports, etc.

All eCRF information is to be completed. If an item is not available or is not applicable, this fact should be indicated. Blank spaces should not be present unless otherwise directed.

Investigative site staff will enter patient data into the electronic data capture system Medidata Rave. The analysis data sets will be a combination of these data and data from other sources (e.g., laboratory data).

Clinical data management will be performed in accordance with applicable PPD standards and data cleaning procedures to ensure the integrity of the data, e.g., removing errors and inconsistencies in the data. Adverse events and concomitant medication terms will be coded using MedDRA, an internal validated medication dictionary, and concomitant medications will be coded using WHO Drug Dictionary.

After database lock, each study site will receive a CD-ROM containing all of their site specific eCRF data as entered into Medidata Rave for the study, including full discrepancy and audit history. Additionally, a CD-ROM copy of all of the study site's data from the study will be created and sent to the sponsor for storage. PPD will maintain a duplicate CD-ROM copy for their records. In all cases, patient initials will not be collected or transmitted to the sponsor.

## **8 Ethics**

### **8.1 Independent Ethics Committee or Institutional Review Board**

Federal regulations and the ICH E6(R1) guidelines require that approval be obtained from an IRB/ IEC before participation of human patients in research studies. Before study onset, the protocol, informed consent, advertisements to be used for the recruitment of study patients, and any other written information regarding this study to be provided to the patient or the patient's legal guardian must be approved by the IRB/IEC. Documentation of all IRB/IEC

approvals and of the IRB/IEC compliance with ICH E6(R1) will be maintained by the site and will be available for review by the sponsor or its designee.

All IRB/IEC approvals should be signed by the IRB/IEC chairman or designee and must identify the IRB/IEC name and address, the clinical protocol by title or protocol number or both, and the date approval or a favorable opinion was granted.

The investigator is responsible for providing written summaries of the progress and status of the study at intervals not exceeding 1 year or otherwise specified by the IRB/IEC. The investigator must promptly supply the sponsor or its designee, the IRB/IEC, and, where applicable, the institution, with written reports on any changes significantly affecting the conduct of the study or increasing the risk to patients.

## **8.2 Ethical Conduct of the Study**

The study will be performed in accordance with the ethical principles that have their origin in the Declaration of Helsinki, ICH E6(R1), CFR, and all other applicable regulations.

## **8.3 Patient Information and Consent**

Fully informed consent will be obtained before any study-specific procedures are performed. Country-specific regulations regarding the collection of informed consent and personal data will be followed at each site. It is anticipated by the very nature of the study that many patients who will be eligible for this protocol will not be able to give fully informed consent themselves due to various reasons including sedation or unconscious state. In a situation where a patient is unable to provide consent, the patient's legally authorized representative may provide written consent, as approved by the institutional-specific guidelines. Informed consent may be obtained from an independent consulting physician or obtained on the basis of emergency study protocol by the investigator in countries where regulation and institution guidelines permit. This form of consent can only be used when the patient and legally authorized representative are unable to provide consent. In cases where the initial informed consent is obtained from a legal representative, an independent consulting physician, or by the investigator, the patient must also give written informed consent as soon as they are able.

The investigator shall retain the signed original ICF(s) and give a copy of the signed original form to the patient or legal guardian.

## **9 Investigator's Obligations**

The following administrative items are meant to guide the investigator in the conduct of the study but may be subject to change based on industry and government standard operating procedures, working practice documents, or guidelines. Changes will be reported to the IRB/IEC but will not result in protocol amendments.

### **9.1 Confidentiality**

All laboratory specimens, evaluation forms, reports, and other records will be identified in a manner designed to maintain patient confidentiality. All records will be kept in a secure storage area with limited access. Clinical information will not be released without the written permission of the patient (or the patient's legal guardian), except as necessary for monitoring and auditing by the sponsor, its designee, the FDA, the European Medicines Agency, other regulatory national authorities, or the IRB/IEC.

The investigator and all employees and coworkers involved with this study may not disclose or use for any purpose other than performance of the study any data, record, or other unpublished, confidential information disclosed to those individuals for the purpose of the study. Prior written agreement from the sponsor or its designee must be obtained for the disclosure of any said confidential information to other parties.

### **9.2 Financial Disclosure and Obligations**

Investigators are required to provide financial disclosure information to allow the sponsor to submit the complete and accurate certification or disclosure statements required under 21 CFR 54. In addition, the investigator must provide to the sponsor a commitment to promptly update this information if any relevant changes occur during the course of the investigation and for 1 year following the completion of the study.

Neither the sponsor nor PPD is financially responsible for further testing or treatment of any medical condition that may be detected during the screening process. In addition, in the absence of specific arrangements, neither the sponsor nor PPD is financially responsible for further treatment of the patient's disease.

### **9.3 Investigator Documentation**

Prior to beginning the study, the investigator will be asked to comply with ICH E6(R1) 8.2 and Title 21 of the CFR by providing the following essential documents, including but not limited to:

IRB/IEC approval

Original investigator-signed investigator agreement page of the protocol

Form FDA 1572, fully executed, and all updates on a new fully executed Form FDA 1572

Curriculum vitae for the investigator and each sub-investigator listed on Form FDA 1572

Financial disclosure information to allow the sponsor to submit complete and accurate certification or disclosure statements required under 21 CFR 54. In addition, the investigators must provide to the sponsor a commitment to promptly update this information if any relevant changes occur during the course of the investigation and for 1 year after the completion of the study.

IRB/IEC-approved informed consent and any other written information regarding this study that is to be provided to the patient or legal guardian

Laboratory certifications and normal ranges for any local laboratories used by the site, in accordance with 42 CFR 493

### **9.4 Study Conduct**

The investigator agrees that the study will be conducted according to the principles of ICH E6(R1). The investigator will conduct all aspects of this study in accordance with all national, state, and local laws or regulations. Study information from this protocol will be posted on publicly available clinical trial registers before enrollment of patients begins.

### **9.5 Adherence to Protocol**

The investigator agrees to conduct the study as outlined in this protocol in accordance with ICH E6(R1) and all applicable guidelines and regulations.

### **9.6 Adverse Events and Study Report Requirements**

By participating in this study the investigator agrees to submit reports of SAEs according to the timeline and method outlined in the protocol. In addition, the investigator agrees to submit annual reports to the study site IRB/IEC as appropriate.

## **9.7 Investigator's Final Report**

Upon completion of the study, the investigator, where applicable, should inform the institution; the investigator/institution should provide the IRB/IEC with a summary of the study's outcome and the sponsor and regulatory authority(ies) with any reports required.

## **9.8 Records Retention**

Essential documents should be retained until at least 2 years after the last approval of a marketing application in an ICH region and until there are no pending or contemplated marketing applications in an ICH region or at least 2 years have elapsed since the formal discontinuation of clinical development of the investigational product. These documents should be retained for a longer period, however, if required by the applicable regulatory requirements or by an agreement with the sponsor. It is the responsibility of the sponsor to inform the investigator/institution as to when these documents no longer need to be retained.

## **9.9 Publications**

After completion of the study, the data will be reported at scientific meetings and/or submitted and published in a scientific journal, regardless of the outcome. In these cases, a publication committee will be responsible for these activities and will work with the investigators to determine how the manuscript is written and edited, the number and order of authors, the publication to which it will be submitted, and other related issues.

In principle the company supports publication of results, regardless of the outcome. In order to prevent subgroup publications prior to main publication, data are the property of the sponsor and cannot be published without prior authorization from the sponsor, but data and publication thereof will not be unduly withheld.

## **10 Study Management**

Table 10–1 presents the study administrative details.

## 10.1 Monitoring

### 10.1.1 External Data Monitoring Committee

An independent DMC will review the results of the interim analysis and select the optimum recAP dose for Part 2 of the study (see Section 7.7.5). The DMC will conduct three additional reviews of the safety data by teleconference once the first 7 days of laboratory data are available for the following: 75 patients in Part 1, 60 patients in Part 2, and 125 patients in Part 2. In each case, the milestone will be patients with at least 7 days of laboratory data. Additional electronic reviews will be conducted of unblinded AE listings after 25, 50 and 100 patients in Part 1 and 30 and 90 patients in Part 2. The DMC can also request ad hoc

reviews. Accumulating safety and efficacy data will be reviewed at predefined milestones during Part 1 and Part 2 of the study by the independent DMC as described in the DMC charter as follows:

- Electronic Review 25 subjects
- Electronic Review 50 subjects
- Teleconference 75 subjects
- Electronic Review 100 subjects
- Face to Face Meeting-interim analysis-120 subjects
- Ad hoc Review- (if needed) between 90-120 additional subjects
- Teleconference 60 additional subjects from Part 2 (at least 180 total)
- Electronic Review 90 additional subjects from Part 2 (at least 210 total)
- Teleconference 125 additional subjects from Part 2 (at least 245 total)
- Ad hoc Review- (if needed) between 125-170 subjects from Part 2 (at least 245-290 total).

### **10.1.2 Monitoring of the Study**

The clinical monitor, as a representative of the sponsor, has the obligation to follow the study closely. In doing so, the monitor will visit the investigator and study site at periodic intervals, in addition to maintaining necessary phone and letter contact. The monitor will maintain current personal knowledge of the study through observation, review of study records and source documentation, and discussion of the conduct of the study with the investigator and personnel.

All aspects of the study will be carefully monitored, by the sponsor or its designee, for compliance with applicable government regulation with respect to current ICH E6(R1) and current standard operating procedures.

### **10.1.3 Inspection of Records**

Investigators and institutions involved in the study will permit study-related monitoring, audits, IRB/IEC review, and regulatory inspections by providing direct access to all study records. In the event of an audit, the investigator agrees to allow the sponsor, representatives of the sponsor, or a regulatory agency (e.g., FDA or other regulatory agency) access to all study records.

The investigator should promptly notify the sponsor and PPD of any audits scheduled by any regulatory authorities and promptly forward copies of any audit reports received to the sponsor.

## **10.2 Management of Protocol Amendments and Deviations**

### **10.2.1 Modification of the Protocol**

Any changes in this research activity, except those necessary to remove an apparent, immediate hazard to the patient, must be reviewed and approved by the sponsor or its designee. Any protocol amendments will be prepared by the sponsor/contract research organization. Protocol amendments will be submitted to the IRB/EC and to regulatory authorities in accordance with local regulatory requirements. Approval must be obtained from the IRB/EC and regulatory authorities (as locally required) before implementation of any changes, except for changes necessary to eliminate an immediate hazard to patients or changes that involve logistical or administrative aspects only (e.g., change in Medical Monitor or contact information).

### **10.2.2 Protocol Deviations**

The investigator or designee must document and explain in the patient's source documentation any deviation from the approved protocol. The investigator may implement a deviation from, or a change of, the protocol to eliminate an immediate hazard to study patients without prior IRB/IEC approval. As soon as possible after such an occurrence, the implemented deviation or change, the reasons for it, and any proposed protocol amendments should be submitted to the IRB/IEC for review and approval, to the sponsor for agreement, and to the regulatory authorities, if required.

A deviation from the protocol is an unintended or unanticipated departure from the procedures or processes approved by the sponsor and the IRB/IEC and agreed to by the investigator. A significant deviation (violation) occurs when there is non-adherence to the protocol by the patient or investigator that may result in an additional risk to the patient or which may confound analysis of study results. Significant deviations can include non-adherence to inclusion or exclusion criteria, enrollment of the patient, or non-adherence to FDA regulations or ICH E6(R1) guidelines, and may lead to the patient being withdrawn from the study (see Section 4.2).

Protocol deviations (and violations) will be documented by the clinical monitor throughout the course of monitoring visits. Investigators will be notified in writing by the monitor of deviations. The IRB/IEC should be notified of all protocol deviations in a timely manner.

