### **4.2.1 Reasons for Withdrawal/Discontinuation**

Patients may withdraw from the study at any time and for any reason without prejudice to their future medical care by the investigator or at the study site. Investigators should attempt to determine the cause of withdrawal and, if agreed by the patient, to let the patient return for the Day 90 visit (last safety follow-up visit). The extent of a patient's withdrawal from the study (i.e., withdrawal from further study treatment, withdrawal from active participation in the study, withdrawal from any further contact) should be documented in the eCRF. Efforts should be made to follow-up the randomized and withdrawn patients as much as possible, i.e., to the extent that the patients agree to.

Treatment with study drug will be stopped for any of the following reasons:

1. Any clinical adverse event (AE), laboratory abnormality, or intercurrent illness which, in the opinion of the investigator, indicates that continued treatment with study drug is not in the best interest of the patient.
2. The patient withdraws consent or the investigator or sponsor decide to discontinue the patient's participation in the study.
3. AM-Pharma B.V. terminates the study

Additionally, treatment with study drug may be stopped in case of protocol non-compliance or violations. In this case, the investigator will contact the Medical Monitor to discuss risk/benefit balance of continued treatment with study drug.

In case study drug administration is discontinued prematurely the patient will preferably continue follow-up in the study as per protocol for safety and to allow for intent-to-treat (ITT) analysis. If study drug administration is interrupted for any reason, re-starting of study drug should be discussed with the Medical Monitor.

The reason for and date of study drug discontinuation and/or the reason for and date of withdrawal from the study must be recorded in the electronic case report form (eCRF). If study drug is discontinued because of an AE or a clinically significant abnormal laboratory test result, evaluations will continue until the event has resolved or stabilized or until a determination of a cause unrelated to the study drug or study procedure is made. The specific event or laboratory finding(s) must be documented.

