#### **6.3.14.1 Definitions of Adverse Events**

An AE is defined as any untoward medical occurrence (e.g., symptom, sign, diagnosis or diagnostic test finding) in a patient enrolled into a clinical study regardless of its causal relationship to study drug.

A TEAE is defined as any event not present before exposure to study drug or any event already present that worsens in either intensity or frequency after exposure to study drug.

An SAE is defined as any event that results in death, is immediately life threatening, requires inpatient hospitalization or prolongation of existing hospitalization, results in persistent or significant disability/incapacity, or is a congenital anomaly/birth defect. Important medical events that may not result in death, be life threatening, or require hospitalization may be

considered SAEs when, based upon appropriate medical judgment, they may jeopardize the patient or may require medical or surgical intervention to prevent one of the outcomes listed in this definition. Medical and scientific judgment should be exercised in deciding whether expedited reporting is appropriate in other situations, such as important medical events that may not be immediately life threatening or result in death or hospitalization but may jeopardize the patient or may require intervention to prevent one of the other outcomes listed in the aforementioned definition. These should also be considered serious. A death occurring during the study or which comes to the attention of the investigator until Day 28 visit, whether considered treatment related or not, must be reported as an SAE. In the event of an SAE the investigator may immediately stop treatment (during the treatment phase, i.e., the first 3 days of the study) if it is considered in the best interest of the patient. In case study drug is discontinued early, the patient will continue follow-up in the study as per protocol. If interrupted for any reason, re-starting of study drug should be discussed with the Medical Monitor (see Section 4.2.1).

Any medical condition that is present at the time that the patient is screened but does not deteriorate should not be reported as an AE. However, if the medical condition deteriorates at any time during the study, it should be recorded as an AE.

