5.1. Disposition

Patient disposition will be summarized for the all Enrolled Set. A disposition of patients includes the number and percentage of patients for the following categories: patients who were not randomly assigned to treatment, patients in the ITT Combined Set, patients treated (Safety Set), patients in the PP Day 1-7 Combined Set, patients in the PP Day 1-7 Part 1 Analysis Set, patients in the ITT Part 1 Set, patients in the ITT Part 1 Interim Set, patients in the ITT Part 2 Set, patients in the PP Day 1-7 Part 2 Set, patients in the PK Set and patients in the Iohexol Set. The number and percentage of patients who completed the study and patients who discontinued from the study will be summarized for the ITT Combined Set, the ITT Part 1 Set, ITT Part 1 Interim Set and the ITT Part 2 Set. The percentages will be based on the number of patients in each analysis set.

The reasons for study discontinuation will also be summarized in this table. The reason for study discontinuation includes the following: Adverse Event, Lab abnormality, Patient Withdrew consent, Investigator Decision, Sponsor termination of study, Protocol Non-Compliance or violation, Death and Other. The percentages will be based on the number of patients who discontinued from the study.

The disposition table will be repeated by site for the all Enrolled Set.

Patient disposition data will be presented in a listing.

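### Protocol 10.2.2 allows withdrawal from the study for significant deviations, while 4.2.1 and 6.3.14.1 treat early stopping of study drug as compatible with continued follow-up; the sections need reconciling

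*Protocol*

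**What the plan says.** **Protocol 10.2.2** counts failures of the inclusion or exclusion criteria among the significant deviations, and adds "and may lead to the patient being withdrawn from the study (see Section 4.2").

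**Protocol 4.2.1** opens its list with "Treatment with study drug will be stopped for any of the following reasons". Adverse events, laboratory abnormalities and intercurrent illness are item 1. Item 2 includes the case where "the investigator or sponsor decide to discontinue the patient's participation in the study". Violations come after the list: "Additionally, treatment with study drug may be stopped in case of protocol non-compliance or violations", with the Medical Monitor to be contacted. On what follows, it says: "In case study drug administration is discontinued prematurely the patient will preferably continue follow-up in the study as per protocol for safety", and gives the ITT analysis as a further purpose.

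**Protocol 4.2.2** describes how withdrawals are handled and refers to patients withdrawn because of an AE or SAE.

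**Protocol 6.3.14.1**, in the text on serious adverse events, says: "In case study drug is discontinued early, the patient will continue follow-up in the study as per protocol".

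**SAP 5.1** lists the reasons for study discontinuation to be tabulated: "Adverse Event, Lab abnormality, Patient Withdrew consent, Investigator Decision, Sponsor termination of study, Protocol Non-Compliance or violation", then death and other.

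**Handling of the lost data.** Withdrawn patients are not replaced (Protocol 4.2.3). Missing daily clearances are interpolated where possible, otherwise carried forward (Protocol 7.1, SAP 8.1). A patient who dies or withdraws without recorded RRT counts as not having required it (Protocol 7.2, SAP 8.2.1).

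**The concern.** Stopping study drug and leaving the study are different events, and an ITT analysis depends on keeping them apart. A site that discovers an eligibility failure after randomisation finds one instruction in 10.2.2 and another in 4.2.1. If it follows 10.2.2, it may end observation of a patient who has not withdrawn consent.

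Dosing is finished by Day 3, the primary endpoint runs to Day 7 and the key secondary endpoint to Day 28, so an early exit can leave most of both endpoints unobserved. The gap is then filled by LOCF for AUC1-7 and by a score of no RRT for the key secondary endpoint. Loss of this kind is avoidable, because it comes from the wording and not from the patient's choice.

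**Working it through.** **1. The passages side by side.** Take a consenting patient found on Day 2 to have failed an eligibility criterion.

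| Section | Study drug | Follow-up |
|---|---|---|
| 10.2.2 | not addressed | patient may be withdrawn from the study |
| 4.2.1 | may be stopped, Medical Monitor contacted | preferably continues |
| 6.3.14.1 | case where drug is stopped early | continues, no qualifier |

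The reference from 10.2.2 leads to a section without a deviation-specific withdrawal rule. The nearest text is 4.2.1 item 2, which gives no criteria and sits inside the list of reasons to stop drug.

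**2. Intent.** Protocol 14.1.8.1 gives the reason for the Amendment 1 change to 4.2.1: leaving the study is not the same as stopping drug. Section 10.2.2 does not reflect this. Exclusion 17 bars patients whose AKI diagnosis is more than 24 hours old at dosing, yet SAP 8.1.5 provides a category of 24 hours or more, so the analysis allows for such patients. Significant deviations already lead to exclusion from the per-protocol sets (Protocol 7.5, SAP 4.3.3), so the analysis does not need them withdrawn.

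**3. Path of the lost data.** After withdrawal following Day 2, no later daily value exists to interpolate towards. Days 3 to 7, five of seven, are carried forward, and up to 28 - 2 = 26 days of the RRT period are unobserved. Withdrawal after Day 7 does not touch AUC1-7. The sensitivity analysis meant to examine LOCF (SAP 8.1.4) excludes patients who died before Day 8, not those who withdrew.

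**4. The plan's power, reproduced.** Inputs from Protocol 7.4: SD 49 mL/min, placebo 60, recAP 60 to 79, n1 = 30 in each of four arms, n2 = 85 in each of two, 1-sided 2.5%. From 7.7.6: stop if all three 1-sided p-values exceed 0.8. From 7.7.1:

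Z = sqrt(30/115) × Φ⁻¹(1 - p1) + sqrt(85/115) × Φ⁻¹(1 - p2), with p1 Dunnett-adjusted; reject if Z > 1.96.

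The simulation used t tests without a site term and the best dose selected, with 100,000 runs per power scenario and 400,000 under the null.

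| Scenario (low / medium / high dose mean) | Simulated | Stated |
|---|---|---|
| 60 / 79 / 79 | 81.3% | 79% to 86% |
| 69.5 / 79 / 79 | 79.3% | 79% to 86% |
| 79 / 79 / 79 | 85.8% | 79% to 86% |
| only the high dose strong (three variants) | 65.9% to 68.8% | 66% to 67% |
| null | 2.5% | 2.4% |

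The plan's figures reproduce. The exact high-dose-only scenarios are not given. The null gap is within Monte Carlo error of the plan's 50,000 runs (SE about 0.07 points).

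**5. Effect of early loss on power.** The documents give no withdrawal rate, so w, the share lost early in each arm, is an assumption. In the worst case for dilution, the carried-forward value holds none of the 79 - 60 = 19 mL/min effect. With the SD unchanged, the difference becomes d = 19 × (1 - w).

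| w | d (mL/min) | Power, 60 / 79 / 79 | Power, 79 / 79 / 79 |
|---|---|---|---|
| 0 | 19.00 | 81.7% | 85.4% |
| 2% | 18.62 | 80.1% | 84.2% |
| 5% | 18.05 | 77.2% | 81.9% |

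The first row is a fresh run, hence the small differences from step 4. In the last two columns, both active means of 79 are replaced by 60 + d.

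**6. Effect on RRT incidence.** If a share w withdraws and a share q of these would later have needed RRT, scoring them as no RRT understates incidence by w × q. With assumed values this is 0.02 × 0.30 = 0.6 points to 0.05 × 0.60 = 3.0 points.

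**The case against.** The strongest reply is that the protocol already protects follow-up. Section 4.2.1 asks for withdrawn patients to be followed as far as they agree and for the extent of withdrawal to be documented. Section 4.2.2 prefers Day 28 assessments at exit, seeks a Day 90 visit and keeps all data from withdrawals in the ITT analysis. The RRT analysis is repeated without deaths and withdrawals, and the per-protocol sets, which allow at most two missing clearances, drop early exits. The clause in 10.2.2 is also permissive, and nothing shows that it would be used often.

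Much of this stands, and it limits the likely size. It does not recover the data: one assessment at exit does not replace daily clearances to Day 7, and the repeat RRT and per-protocol analyses remove these patients without learning their outcomes.

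Four stronger readings are not supported:

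- A reader might infer that SAP 5.1 lets sites withdraw patients for adverse events or laboratory abnormalities. It is a list of table categories and authorises nothing.
- A reader might take Section 4.2 as concerned with drug only. Item 2 of 4.2.1 and the text of 4.2.2 both contemplate study withdrawal, so part of the conflict lies within 4.2.
- A reader might expect exits to differ by arm and bias the comparison. The trial is double-blind and no passage shows differential withdrawal.
- A reader might set one patient's LOCF error against the planned effect. On an invented course of 20, 30, ..., 80 mL/min the mean is 50, and LOCF after Day 2 gives (20 + 6 × 30)/7 = 28.6, an error of 21.4. The 19 mL/min is a difference between group means; that patient moves the mean of a 115-patient arm by 21.4/115 = 0.19 mL/min.

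**Conclusion.** The inconsistency is real and in current text. Section 10.2.2 offers study withdrawal for deviations and points to a section without such a rule, 4.2.1 prefers continued follow-up, and 6.3.14.1 states it outright. Item 2 of 4.2.1 and Section 4.2.2 leave the same route open, and SAP 5.1 blurs the two kinds of discontinuation in reporting. The resulting gaps feed LOCF and the no-RRT score, and the planned LOCF sensitivity analysis does not test them.

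The size cannot be found in the documents. If 2% to 5% per arm were lost early, equally in both arms, with none of the effect retained and the SD unchanged, power would fall by about 1 to 5 points. How much of any loss would be avoidable is unknown. This is a wording fault worth correcting because the correction is cheap. It does not show that the trial is biased or materially underpowered.

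**What to change.** 1. **Protocol 10.2.2:** replace the withdrawal clause with: may lead to exclusion from the per-protocol set; the patient remains in follow-up unless consent is withdrawn.
2. **Protocol 4.2.1, 4.2.2 and 6.3.14.1:** reconcile them so that follow-up continues after drug is stopped for every patient who has not withdrawn consent. For item 2 of 4.2.1 this concerns study participation only.
3. **SAP 5.1 and the eCRF:** report study-drug discontinuation and study withdrawal separately, each with its own reasons, and add a loss-to-follow-up category. Protocol 4.2.2 describes when a patient is considered lost, but the SAP list has no such entry.

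The rules for stopping study drug are unchanged, and patients keep the right to withdraw. The cost is protocol and SAP wording, a revised eCRF reason list and a few more follow-up visits, with no added procedures.
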